## 6.3.2. Breaking the Blind

The method for breaking the blind in this study will be manual. In case of an emergency, the investigator has the sole responsibility for determining if unblinding of a participant's treatment assignment is warranted. Participant safety must always be the first consideration in making such a determination. If the investigator decides that unblinding is warranted, the investigator should make every effort to contact the sponsor prior to unblinding a participant's treatment assignment unless this could delay further management of the participant. If a participant's treatment assignment is unblinded, the sponsor must be notified within 24 hours after breaking the blind. When the blinding code is broken, the reason must be fully documented in a CRF.

Blood specimens will be obtained from all participants for PK analysis to maintain the study blind at the investigator site. Only the investigator site staff and blinded study monitor, if assigned, will be blinded to study treatment. A limited number of Pfizer study team personnel will be unblinded to participant treatments in order to permit real-time interpretation of the safety and PK data; and provide information necessary to potentially alter the dose escalation sequence. The blinded study monitor, if assigned, will remain blinded to treatment until all monitoring for the study has been completed. Specimens from participants randomized to placebo will not be routinely analyzed. To minimize the potential for bias, treatment randomization information will be kept confidential by Pfizer unblinded personnel and will not be released to the blinded investigator or blinded investigator site personnel until the study database has been locked or the investigator requests unblinding for safety reasons.

## **6.4. Study Intervention Compliance**

When participants are dosed at the site, they will receive study intervention directly from the investigator or designee, under medical supervision. The date and time of each dose administered in the clinic will be recorded in the source documents and recorded in the CRF. Study site personnel will examine each participant's mouth to ensure that the study intervention was ingested.

### 6.5. Concomitant Therapy

Use of prescription or nonprescription drugs and dietary and herbal supplements are prohibited within 7 days or 5 half-lives (whichever is longer) prior to the first dose of study intervention. Limited use of nonprescription medications that are not believed to affect participant safety or the overall results of the study may be permitted on a case-by-case basis following approval by the sponsor. Acetaminophen/paracetamol may be used at doses of  $\leq 1$  g/day.

Females using hormonal contraceptives or taking hormone replacement therapy may be eligible to participate in this study if they are willing to discontinue therapy at least 28 days prior to the first dose of study treatment and remain off hormonal therapy for the duration of the study. Depo-Provera® must be discontinued at least 6 months prior to the first dose of study treatment. Hormonal contraceptives that meet the requirements of this study are allowed to be used in participants who are WOCBP (See Appendix 4).

All concomitant treatments taken during the study must be recorded with indication, daily dose, and start and stop dates of administration. All participants will be questioned about concomitant treatment at each clinic visit.

Treatments taken within 28 days before the first dose of study intervention will be documented as a prior treatment. Treatments taken after the first dose of study intervention will be documented as concomitant treatments.

### 6.5.1. Rescue Medicine

There is no rescue therapy to reverse the AEs observed with study intervention; standard medical supportive care must be provided to manage the AEs.

### 6.6. Dose Modification

Progression to the next dose in PART-1 will occur if the last dose was well tolerated and after satisfactory review of the available safety and PK data. Each dose escalation will be based on review of the safety data up to a minimum of 48-hours post dose plus PK assessments up to 6-hours post dose, in at least 3 actively treated participants and at least 1 placebo-treated participant dosed in the previous dose-level.

Progression to the next dose in PART-2 will occur if the last dose was well tolerated and after satisfactory review of the available safety and PK data. Each dose escalation will be based on review of the safety data up to a minimum of 6-days plus PK assessments up to 6-hours post dose on Day 5, in at least 3 actively treated participants and at least 1 placebo-treated participant dosed in the previous dose-level.

### 6.6.1. Dose Escalation and Stopping Rules

Dose escalation stopping rules will be used to determine whether the maximal tolerated dose has been attained. Dose escalation may be stopped if it is determined that the limits of safety and/or tolerability have been reached. This decision will be made after a discussion takes place between the sponsor study team and the investigator. The sponsor study team may not overrule the investigator's decision to stop dose escalation. If dose escalation is stopped because of any of these criteria, additional cohorts may receive the same or lower doses of the study intervention.

The dose escalation will be terminated based on the following criteria:

- If 50% or more of the participants receiving active drug at a given dose level (but not participants receiving placebo) develop similar clinically significant laboratory, ECG, or vital sign abnormalities, in the same organ class, indicating dose-limiting intolerance.
- Severe nonserious AEs, considered as, at least, possibly related to study intervention administration, in 2 participants at a given dose level (but not participants receiving placebo), independent of within or not within the same system organ class, indicating dose-limiting intolerance.

- Dosing will be paused for any SAE that occurs in a participant receiving active treatment until causality is fully assessed by the PI and sponsor. Dosing may resume if the SAE is determined to be not drug-related by the PI and sponsor. If the SAE is determined to be either drug-related or unknown, either dosing will cease or the SAE will be evaluated by the sponsor's protocol review committee (or similar review group), which is independent of the study team and investigators. If the protocol review committee determines that dosing may resume, a plan that mitigates risks to participants with the resumption of dosing will be implemented. Such a plan could include a revision of inclusion/exclusion criteria, repeating or reducing the dose, or adding appropriate safety monitoring.
- It is determined that the limit of safety and/or tolerability has been reached. This decision will be made following discussions between the study team and the investigator.
- Other findings that, at the discretion of the study team and investigator, indicate that dose escalation should be halted.
- If, at any dose level, the average exposure reaches or exceeds the PK stopping limits, total plasma AUC (AUCinf in PART-1 and PART-5 and AUCtau in PART-2) and Cmax of CO μg•h/mL and CO μg/mL.
- If, based on the observed data, the group mean  $C_{max}$  or AUC (based on total plasma concentration) of the next planned dose is projected to exceed the escalation limits, that dose will not be explored. Modified doses may be explored if they are not expected to exceed PK stopping criteria.

Progression to the next dose will occur if the last dose was well tolerated and after satisfactory review of the available safety and PK data.

### 6.7. Intervention After the End of the Study

No intervention will be provided to study participants at the end of the study.

# 7. DISCONTINUATION OF STUDY INTERVENTION AND PARTICIPANT DISCONTINUATION/WITHDRAWAL

## 7.1. Discontinuation of Study Intervention

In rare instances, it may be necessary for a participant to permanently discontinue study intervention (definitive discontinuation). Reasons for definitive discontinuation of study intervention include the following

- AE requiring discontinuation in investigator's view;
- Pregnancy;

### • Positive COVID-19 test.

If study intervention is definitively discontinued, the participant will not remain in the study for further evaluation. See the SoA for data to be collected at the time of discontinuation of study intervention.

In the event of discontinuation of study intervention, it must be documented on the appropriate CRF/in the medical records whether the participant is discontinuing further receipt of study intervention or also from study procedures, posttreatment study follow-up, and/or future collection of additional information.

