| Urine samples for:   |                |           |                       |       |       |       |                       |                |       |                |       |                        |        |           |                             |    |
| Drug screen testing  | X              | X         |                       |       |       |       |                       |                |       |                |       |                        |        |           |                             |    |
| Urinalysis°  | X              | X         |                       | X     |       |       | X                     | X              |       | X              |       | X                      |        | X         |                             | X  |
| Pharmacokinetics   |                |           | X                     |       |       |       |                       |                |       |                |       | X                      |        |           |                             |    |

- a. Visit Identifier: Day relative to start of study treatment (Day 1).
- b. F/U Contact: Follow-up contact may occur via telephone and must occur 28 to 35 days after the last dose of investigational product.
- c. SARS-CoV-2 RT-PCR: Screening, admission (Day -1), 4 days following admission (Day 4), ad hoc test based on symptoms, and for ambulatory on-site visits.
- d. CRU Confinement: Participants will be required to stay at CRU from Day-1 until completing Day 12 activities.
- e. **Physical Examination:** Complete physical examination will be conducted at Screening or upon admission (Day -1). Brief physical examination may be performed at other times, as appropriate, for findings during previous examination or new/open AEs, at investigator's discretion.
- f. Vital signs and 12-lead ECG: Except on D1, D5 and D10, all vital signs and ECGs are to be collected pre-dose. on D12, collected 48h after last dose of PF-07321332/placebo.
- g. **Study drug administration:** From Day 1 Day 9 at approximately 0, 8 and 16 h for TID regimen (ie, every 8 h) of PF-07321332/placebo alone and at 0 and 12h for BID regimen (ie, every 12h). On Day 10, at approximately 0h for TID or BID regimen of PF-07321332/placebo. The study drug should be administered after approximately at least 7h of fast in the morning dose (0h) and at least 2 hours of fast for afternoon and/or evening doses. For dosing in fed condition, please refer Section 5.3.1.

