Dose escalation, if required, to subsequent dose levels (Treatment Q) in Periods 3 and 4 will be based on all available (a minimum of 48 hours post-dose) safety data and PK data over approximately ≥6 hours (after the first dose on Day 1) in Period 1.

The dose escalation stopping criteria are specified in Section 6.6.1. The total daily dose in this part will not exceed 3000 mg.

In PART-1 and PART-2 of the study, the dose levels, frequency of administration and/or meal condition may be changed based on emerging PK and safety data. During the SAD and MAD the dose increments and planned doses may be adjusted, as the study progresses dependent upon emerging PK, safety, and tolerability data. Other intermediate doses or lower doses may be administered instead of the planned doses, or changes in dosing frequency or titration schemes may be proposed for MAD cohorts if safety/tolerability or PK issues become apparent, if evidence of nonlinear PK dictates the need to escalate more slowly, or if subsequent doses are predicted to result in exposures that exceed the target limits. Any potential altered dose scheme will be equal to or less than a 3.3-fold increase in exposure from the previous highest dose if a higher dose is warranted to achieve exposure. If gastrointestinal tolerability issue becomes dose-limiting in PART-1 or 2, dosing with food (standard meal) or pre-dosing with anti-emetics may be considered. The projected average exposure of the altered dose scheme will not exceed the exposure limit specified in Section 6.1.1.

In all cohorts (all parts of the study), participants can be released after completing activities specified in SoA. A telephone follow-up contact will occur between 28 to 35 days after the day of last administration of study intervention. At the discretion of the investigator, telephone follow-up contact may be substituted with an on-site visit in case of additional follow-up of open AEs or clinically significant laboratory findings.

The total planned duration of participation, from Screening visit to the Follow-up phone call, may be approximately 12 weeks for PART-1 and PART-5, 10 weeks for PART-2 and PART-3 and 8 weeks for PART-4.

Participants who discontinue from the study (due to non-safety reasons) may be replaced at the Sponsor's discretion.

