### 7.2.1. Withdrawal of Consent

Participants who request to discontinue receipt of study intervention will remain in the study and must continue to be followed for protocol-specified follow-up procedures. The only exception to this is when a participant specifically withdraws consent for any further contact with him or her or persons previously authorized by the participant to provide this information. Participants should notify the investigator in writing of the decision to withdraw consent from future follow-up, whenever possible. The withdrawal of consent should be explained in detail in the medical records by the investigator, as to whether the withdrawal is only from further receipt of study intervention or also from study procedures and/or posttreatment study follow-up, and entered on the appropriate CRF page. In the event that vital status (whether the participant is alive or dead) is being measured, publicly available information should be used to determine vital status only as appropriately directed in accordance with local law.

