## 8.3.1. Time Period and Frequency for Collecting AE and SAE Information

The time period for actively eliciting and collecting AEs and SAEs ("active collection period") for each participant begins from the time the participant provides informed consent, which is obtained before the participant's participation in the study (ie, before undergoing any study-related procedure and/or receiving study intervention), through and including a minimum of 28 calendar days after the last administration of the study intervention.

Follow-up by the investigator continues throughout and after the active collection period and until the AE or SAE or its sequelae resolve or stabilize at a level acceptable to the investigator and Pfizer concurs with that assessment.

For participants who are screen failures, the active collection period ends when screen failure status is determined.

If the participant withdraws from the study and also withdraws consent for the collection of future information, the active collection period ends when consent is withdrawn.

If a participant definitively discontinues or temporarily discontinues study intervention because of an AE or SAE, the AE or SAE must be recorded on the CRF and the SAE reported using the CT SAE Report Form.

Investigators are not obligated to actively seek AE or SAE after the participant has concluded study participation. However, if the investigator learns of any SAE, including a death, at any time after a participant has completed the study, and he/she considers the event to be reasonably related to the study intervention, the investigator must promptly report the SAE to Pfizer using the CT SAE Report Form.

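### Protocol 7.1 takes a participant definitively off study drug out of the study, which contradicts its own next paragraph, the 28-day AE window and the 28–35 day contact; limit the sentence to dosing

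*Protocol*

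**What the plan says.** Protocol Section 7.1 gives three reasons for definitive discontinuation: an AE that in the investigator's view requires it, pregnancy, and a positive COVID-19 test. The list is introduced as inclusive rather than complete. The consequence is stated without qualification: "If study intervention is definitively discontinued, the participant will not remain in the study for further evaluation". The next sentence points to the schedule of activities for data due at the time of stopping. The paragraph after that requires the site to document "whether the participant is discontinuing further receipt of study intervention or also from study procedures, posttreatment study follow-up, and/or future collection of additional information".

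The other current text on follow-up after the last dose is:

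- **Section 7.2.1:** "Participants who request to discontinue receipt of study intervention will remain in the study and must continue to be followed for protocol-specified follow-up procedures". A single exception is stated: withdrawal of consent for further contact.
- **Section 8.3.1:** active AE/SAE collection for each participant starts at consent and runs "through and including a minimum of 28 calendar days after the last administration of the study intervention". The stated early ends are screen failure and the case where a participant leaves the study and also "withdraws consent for the collection of future information, the active collection period ends when consent is withdrawn". The section adds: "Investigators are not obligated to actively seek AE or SAE after the participant has concluded study participation".
- **Section 4.1, for all parts:** "A telephone follow-up contact will occur between 28 to 35 days after the day of last administration of study intervention".
- **Table 2 footnote b, for PART-2:** "Follow-up contact may occur via telephone and must occur 28 to 35 days after the last dose of investigational product".

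**The concern.** Taken at face value, the 7.1 sentence ends a person's participation when dosing is permanently stopped, while the rest of the protocol counts safety follow-up from the last dose whatever the reason for stopping. A site cannot obey both. The participants most clearly within 7.1 are those stopped because of an AE, in whom later safety information matters most.

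The route to harm is narrow. A site reads 7.1 as concluding participation. It then relies on the line in 8.3.1 that removes the duty to seek events actively once participation has concluded, and so does not ask about new events up to 28 days after the last dose. TEAEs and withdrawals due to TEAEs are primary endpoints in PART-1, PART-2 and PART-5. With about 4 participants on active drug per dose level in PART-1 and PART-2, each safety record carries weight. SAP Section 3.5.1 flags events from first dose until the end of the study as treatment-emergent, so the analysis presumes that collection continues.

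**Working it through.** This is a check of text consistency. No power, alpha or precision figure is involved; the only arithmetic is on the contact window.

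**Step 1. Is follow-up anchored to the last dose?** The formula is contact window = last-dose day + 28 to last-dose day + 35.

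- PART-2, plan's own figure: last PF-07321332/placebo dose on Day 10. 10 + 28 = 38 and 10 + 35 = 45. Table 2 shows Day 38–45, so the figure is reproduced.
- PART-1, plan's own figure: dose on Day 1 of the period. 1 + 28 = 29 and 1 + 35 = 36. Table 1 shows Day 29–36, so the figure is reproduced.

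The anchor is therefore the last dose, and the rule works equally for someone who stops early.

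**Step 2. Apply the rule to an early stop.** Assume, for illustration only, a PART-2 participant whose last dose is on Day 3. AE collection runs to at least 3 + 28 = Day 31, and the contact falls between Day 31 and 3 + 35 = Day 38. Read literally, 7.1 removes this participant before either. The number of uncovered days cannot be computed, because the protocol gives no interval between stopping drug and the early termination visit.

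**Step 3. Set the rules side by side for a participant stopped for an AE with consent intact.**

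| Text | Instruction |
|---|---|
| 7.1, consequence sentence | Leaves the study |
| 7.1, next paragraph | Record whether the stop is drug only or also follow-up, so staying is possible |
| 8.3.1 | AE/SAE collection to at least 28 days after last dose; a drug stop is not listed as an early end |
| 4.1, with Table 2 footnote b for PART-2 | Contact 28–35 days after last dose |

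The first row disagrees with each of the other three. Section 4.1 and the Table 2 footnote describe the same contact, so they count as one rule.

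**Step 4. Section 7.2.1.** It keeps in follow-up those who ask to stop drug. The reasons listed in 7.1 are medical, so the two sections may cover different triggers. If a request can count as definitive discontinuation, which the open list allows, the same person gets opposite instructions. If it cannot, a literal reading gives someone stopped for toxicity less follow-up than someone who chooses to stop. Either way the fit is poor, but the finding does not depend on 7.2.1.

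**Step 5. What is already protected.**

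- Section 8.3.3 requires proactive follow-up of a reported AE until it resolves, stabilizes or is otherwise explained.
- Section 8.3.5.1 follows a pregnancy to its completion.
- Section 7.1 itself brings suspected kidney-injury cases back for evaluation.
- Section 7.2 provides an early discontinuation visit where possible and refers to the schedule for follow-up.

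Only the active search for new events after the stop is left exposed.

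**The case against.** The strongest defence is that the protocol as a whole does not let a site drop anyone. Planned participation is described as running from screening to the follow-up call, so participation has not concluded when dosing stops, and the release from actively seeking events applies only after the call. The 8.3.1 window covers each participant and does not list a drug stop as an early end. The schedule shows AE monitoring in both the follow-up and early termination columns. On this view, further evaluation in 7.1 means only the remaining dosing periods and scheduled PK and ECG assessments.

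That is probably the intent, and it keeps the severity low. It does not rescue the sentence, which says the participant leaves the study and states no such limit. The pointer that follows covers data at the time of stopping, not the later contact.

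Three stronger readings are tempting and are not supported:

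- A reader might infer that 7.1 and 7.2.1 flatly contradict each other. They may cover different triggers, so that conflict is conditional.
- A reader might infer that the AE which caused the stop goes unfollowed, or that TEAE incidence will be biased. Section 8.3.3 covers the first, and nothing in the documents quantifies the second.
- A reader might infer that 7.2 must also change, because it takes the person off both drug and study. That section concerns withdrawal from the study, and the statement is correct for that group.

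**Conclusion.** The 7.1 sentence is an internally contradictory rule and is wrong as written. It is a stated instruction rather than missing detail. It conflicts with the next paragraph of 7.1, with the AE/SAE window in 8.3.1, and with the 28–35 day contact; it also sits badly with 7.2.1.

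Severity is low. The exposure is limited to new, later AEs not being actively sought in the rare participant stopped for toxicity, and only at a site that follows 7.1 literally over the other sections. No count of lost events, uncovered days or bias is claimed. The conclusion rests on reading the sentence as it stands and on consent not having been withdrawn. The Day 3 example is an assumption used only to show how the window moves with the last dose.

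**What to change.** Replace the consequence sentence in Protocol Section 7.1 with wording limited to dosing:

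*The participant will receive no further study intervention; unless consent is withdrawn, the participant completes the early termination assessments, AE/SAE collection for at least 28 days after last dose (Section 8.3.1) and the 28–35 day follow-up contact.*

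No change to Section 7.2 is needed, and participants need not complete the remaining inpatient schedule. The cost is one sentence of protocol text. The early termination assessments, the AE window and the contact are already planned, so no visits, inpatient days or procedures are added.
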